8.8.2 Optional Samples

Upon consent, the following optional samples for biomarker research should be collected from participants as outlined in the SoAs (Section 1.3), with respect to the analyses described in Section 8.7).

- Tongue scrape and stool samples for the assessment of the participant's oral and gut microbiome as well as calprotectin detection
 - Dietary intake is a central determinant of changes in the microbiota. A nutritional assessment will therefore be performed as indicated in the SoAs to better correlate the profiles of the microbiota for participants who consent to provide these optional samples.
 - Screening samples of participants who are not enrolled in the study will be destroyed.
- Fresh tumor biopsies at baseline and as indicated in the SoAs:
 - Collection of tumor biopsies should be guided by ultrasound, CT scan, or other methods according to the location of the selected lesion using a 16-gauge needle (preferred) to provide cores, ideally, of at least 20 mm in length or equivalent size. Ideally, 4 (minimum 2) core biopsies should be obtained at each time-point (at the physician's discretion). In order to mitigate the potential risk associated with tumor biopsies, all participants required to have a biopsy must have tumor lesions from which biopsies can be safely obtained, as per clinical judgment of the treating physician.
 - Fresh screening samples should generally be collected after eligibility is confirmed. Post-dose samples can be collected + 2/- 1 day(s) from scheduled time-point. If the participant progresses and discontinues treatment prior to the on-treatment biopsy day, the tumor biopsy should be taken at the time of treatment discontinuation. An additional biopsy at the time of PR, stable disease, progression, or at any other time-point of interest based on participants' course of disease may be taken after discussion between the Investigator and the Sponsor. A minimum interval of 4 weeks is necessary between the collections of optional tumor biopsies.
 - Baseline and on-treatment biopsies should be preferably taken from the same tumor lesion (metastasis) to ensure comparability. If the sample cannot be collected from the same lesion (e.g., lesion disappears after treatment) then preferably the biopsy should be collected from the same organ, if possible.
 - Fine-needle aspiration is not acceptable. The biopsies will be taken from accessible tumor locations, including, but not limited to, skin, lymph nodes, rectum, liver, etc. Bone biopsies and trans-bronchial biopsies are not acceptable.

- Use of available existing biopsies at the sites prior to the participant's entry in the study should be discussed with the Sponsor (i.e., biopsy should have recently been obtained as part of diagnosis biopsy and participants should have not received any tumor treatment after this collection).
- In the event that a fresh biopsy is taken during the screening period and the participant is not enrolled into the study, the fixed and embedded biopsy (FFPE block) can be returned to the site upon site request. The site must confirm that a written consent is obtained from the participant before return request submission to the Sponsor. If the participant does enroll in the study, fresh biopsies will not be returned to the site.
- The Sponsor will continuously assess the need for making the biopsies mandatory, and additional participants may be enrolled to ensure that sufficient paired fresh biopsy samples are evaluable to conclude the intended PD analyses.

The ICF will contain a separate section that addresses the use of remaining samples for optional exploratory research. A separate signature will be required to document a participant's agreement to allow any remaining samples to be used for optional exploratory research.

8.9 SAMPLES FOR RESEARCH BIOSAMPLE REPOSITORY

8.9.1 Overview of the Research Biosample Repository

The Roche RBR is a centrally administered group of facilities for the long-term storage of human biologic samples, including body fluids, solid tissues, and derivatives thereof (e.g., DNA, RNA, proteins, peptides). The collection, storage, and analysis of the RBR samples will facilitate the rational design of new pharmaceutical agents and the development of diagnostic tests, which may allow for individualized drug therapy for patients in the future.

Samples for the RBR will be collected from participants who give specific consent to participate in this optional RBR. Collected RBR samples will be used to achieve the following objectives:

- To study the association of biomarkers with efficacy or progressive disease.
- To identify safety biomarkers that are associated with susceptibility to developing AEs or can lead to improved AE monitoring or investigation.
- To increase knowledge and understanding of disease biology and drug safety.
- To study treatment response, including drug effects and the processes of drug absorption and disposition.
- To develop biomarker or diagnostic assays and establish the performance characteristics of these assays.

8.9.2 Sample Collection

The following samples will be collected for identification of genetic (inherited) biomarkers:

- Saliva for DNA extraction

The following samples will be stored in the RBR and used for research purposes, including, but not limited to, research on biomarkers related to RO7121661, RO7247669, diseases or drug safety:

- Leftover plasma samples
- Leftover serum samples
- Leftover blood samples
- Leftover fresh or archival tumor tissue samples and unstained slides
- Leftover blood samples for DNA extraction
- Leftover genetic material such as DNA and RNA

The samples collected for DNA extraction include, but is not limited to, genomic analysis and may be sent to one or more laboratories for analysis of germline or somatic mutations via WGS, WES, NGS, or other genomic analysis methods.

Genomics is increasingly informing researcher's understanding of disease pathobiology. WGS provides a comprehensive characterization of the genome and, along with clinical data collected in this study, may increase the opportunity for developing new therapeutic approaches. Data will be analyzed in the context of this study but may also be explored in aggregate with data from other studies. The availability of a larger dataset will assist in identification of important pathways, guiding the development of new targeted agents.

Upon RBR consent, samples may be used for DNA extraction to enable whole genome/exome sequencing WGS/WES and other genomic analysis.

Samples may be sent to one or more laboratories for analysis of germline or somatic mutations via WGS/WES, or other genomic analysis methods. WGS and WES provide a comprehensive characterization of the genome and exome, respectively, and, along with clinical data collected in this study, may increase the opportunity for developing new therapeutic approaches or new methods for monitoring efficacy and safety or predicting which patients are more likely to respond to a drug or develop AEs.

Participants will not be identified by name or any other personally identifying information. Data generated from RBR samples will be analyzed in the context of this study but may also be explored in aggregate with data from other studies. The availability of a larger dataset will assist in identification and characterization of important biomarkers and pathways to support future drug development.

For all samples, dates of consent, and sample collection should be recorded on the associated RBR page of the eCRF. Details on processes for collection and shipment of these samples can be found in separate sample documentation.

RBR samples will be stored and used until they are depleted or come to end of their retention period and are thus destroyed. The RBR storage period will be in accordance with the IRB/EC-approved ICF and applicable laws (e.g., Health Authority requirements).

The repository samples will be subject to the confidentiality standards (as described under Confidentiality in [Appendix 1](#)).

8.10 HEALTH ECONOMICS/MEDICAL RESOURCE UTILIZATION AND HEALTH ECONOMICS

Health economics/medical resource utilization and health economics parameters are not evaluated in this study.

8.11 TIMING OF STUDY ASSESSMENTS

8.11.1 Screening and Pre-treatment Assessments

Written informed consent for participation in the study must be obtained before performing any study-specific screening tests or evaluations. ICFs for enrolled participant and for participants who are not subsequently enrolled will be maintained at the study site.

All screening, and all pre-treatment assessments (related to entry criteria), must be completed and reviewed to confirm that participants meet all eligibility criteria. The Investigator will maintain a screening log to record details of all participants screened and to confirm eligibility or record reasons for screening failure.

An Eligibility Screening Form documenting the Investigator's assessment of each screened participant with regard to the protocol's inclusion and exclusion criteria is to be completed by the Investigator and kept at the investigational site.

Screening and pre-treatment assessments will be performed within 28 days prior to randomization, unless otherwise specified. Results of standard-of-care tests or examinations performed prior to obtaining informed consent and within 28 days prior to randomization may be used (and do not need to be repeated for screening).

8.11.2 Assessments during Treatment

Under no circumstances will participants who enroll in this study and have completed treatment as specified be permitted to be allocated a new randomization number and re-enroll in the study.

All assessments must be performed as per SoAs (Section 1.3). Assessments scheduled on the day of study treatment administration should be performed prior to administration of study treatment, unless otherwise noted in the SoAs. PRO questionnaires will be completed before the participant receives any information on disease status, prior to the performance of non-PRO assessments, and prior to the administration of study treatment.

8.11.3 Assessments at Treatment Discontinuation Visit

Participants who discontinue study treatment early will be asked to return to the clinic ≤ 30 days after the final dose of study drug for a follow-up visit. The visit at which response assessment shows progressive disease may be used as the treatment discontinuation visit.

8.11.4 Follow-Up Assessments

As part of the post-treatment follow-up, the sites will provide to the Sponsor every 3 months with an update on survival status and new anti-cancer therapies of each participant who has completed or discontinued from the study. The survival follow-up will be performed for the first time 90 days (± 7 days) post last dose of study treatment and then every 3 months (± 2 weeks). The sites will use a designated section of the eCRF for this purpose. Post-treatment follow-up visits can be done at site, over the phone, or participant medical records. In addition, all participants will be asked to complete PROs every 3 months during the first year post discontinuation.

For participants who discontinue treatment for reasons other than disease progression or loss of clinical benefit tumor assessments are to continue according to schedule until they start new anti-cancer therapy.

After the treatment discontinuation visit, AEs should be followed as outlined in Section 8.3.1 and Section 8.3.3.

8.11.5 Assessments at Unscheduled Visits

If clinically indicated, any sample or assessment specified in the SoAs can be performed any time as unscheduled sample or assessment at the discretion of the Investigator.

In case of Grade 2 IRRs or Grade ≥ 3 IRRs, suspected anaphylaxis, or Grade ≥ 3 suspected imAEs, the assessments as per SoAs (Section 1.3) are to be performed.

STATISTICAL CONSIDERATIONS

The data will be analyzed by the Sponsor and/or designated contract research organization. Any data analysis carried out independently by the Investigator should be submitted to the Sponsor before publication or presentation. The data will be summarized with respect to demographic and baseline characteristics, efficacy, safety, PK, and biomarkers observations and measurements. The core analysis will *focus on the OS comparison of RO7247669 against nivolumab and take place when approximately* [REDACTED] OS events have been observed in these *two arms of the study*. The additional data for any participant continuing to receive study treatment or being followed for survival past this time (as allowed by the protocol) will be further summarized in a subsequent extension report once the study is terminated.

9.1 SAMPLE SIZE DETERMINATION

This study was designed to provide an assessment of the efficacy and safety of RO7121661 and RO7247669. The primary purpose is the estimation of the OS hazard ratios (HR) of RO7247669 against nivolumab.

The planned number of enrolled participants *was* 255, randomized [REDACTED] into 3 arms. *With the decision to stop enrollment into the RO7121661 arm, the study sample size has been re-estimated to reflect the new randomization scheme (new participants will be randomized [REDACTED] to either RO7247669 or nivolumab).* [REDACTED]

9.2 POPULATIONS FOR ANALYSES

For purposes of analysis, the following populations are defined in [Table 8](#).

Table 8 Analysis Populations

Population	Description
Intent-to-treat	All randomized participants will be included in the intent-to-treat population.
Safety	All participants randomized to study treatment and who received any amount of the study treatment, whether prematurely withdrawn from the study or not, will be included in the safety analysis.
Pharmacokinetic	All participants who have received at least one dose of study treatment and who have data from at least one post-dose sample will be included in the PK analysis population. Participants will be excluded from the PK analysis population if they significantly violate the inclusion or exclusion criteria, deviate significantly from the protocol, or if data are unavailable or incomplete which may influence the PK analysis. Excluded cases will be documented together with the reason for exclusion. All decisions on exclusions from the analysis will be made prior to database closure.
Immunogenicity	Participants who had at least one pre-dose or at least one post-dose ADA assessment will be included and analyzed according to the treatment they actually received or were allocated to receive. The relationship between ADA status and safety, efficacy, PK, and biomarker endpoints will be analyzed and reported descriptively via subgroup analyses.
PRO-evaluable population	All randomized participants with a non-missing baseline assessment and at least one post-baseline assessment for the respective PRO will be included in the PRO-evaluable population.

ADA = Anti-drug antibody; PK = Pharmacokinetic; PRO = Patient-reported outcome.

9.3 STATISTICAL ANALYSES

A technical document describing the statistical analyses plan will provide more details on the statistical analyses.

9.3.1 Demographics and Baseline Characteristics

Study enrollment, study drug administration, reasons for study drug discontinuation, and reasons for discontinuation from the study will be summarized by treatment arm. Major protocol deviations, including major deviations with regard to the inclusion and exclusion criteria, will be summarized by treatment arm.

Demographic (including age, sex, and self-reported race/ethnicity) and baseline disease characteristics (e.g., ECOG Performance Status) will be summarized overall and by treatment arm.

Descriptive statistics (mean, median, standard deviation, and range) will be presented for continuous data, and frequencies and percentages will be presented for categorical data, as appropriate.

Baseline measurements are the last available data obtained prior to the participant receiving the study treatment.

9.3.2 Efficacy Analyses

The efficacy analyses will include all participants in the ITT population, with participants grouped according to the treatment assigned at randomization (Table 9).

Descriptive statistics for the various endpoints will be provided for all 3 arms. However, since the primary aim has shifted from comparing the 2 experimental arms to nivolumab to only compare the RO7247669 arm to nivolumab, the statistical models will only include participants assigned to RO7247669 and nivolumab.

Table 9 Efficacy Statistical Analysis Methods

Endpoint	Statistical Analysis Methods
Primary	
OS
 
OS is defined as the time from randomization to death from any cause. Data for participants who are alive at the time of the data cutoff will be censored at the last date they were known to be alive. Data from participants without post-baseline information will be censored at the date of randomization.
 
Kaplan-Meier methods will be used to estimate median OS for each treatment arm and the 95% CIs for median OS will be computed using the Brookmeyer and Crowley method. The stratified Cox proportional hazard model will be used to estimate the hazard ratio for RO7247669 versus nivolumab (i.e., the magnitude of the treatment effect) and the corresponding 95% confidence interval, stratified by the protocol-defined stratification factors.

Secondary	
ORR and DCR based on RECIST
 
ORR is defined as the proportion of participants who have achieved an objective response, characterized by a CR or PR according to RECIST v1.1. Objective response will be evaluated by treatment arm, and participants without post-baseline overall response assessments will be counted as non-responders. DCR is defined as ORR + stable disease rate (SDR).
 
An estimate of ORR for each treatment group as well as of the difference between the ORR of each experimental arm compared with the active comparator will be computed along with its 95% CI. The Mantel-Haenszel test will be used to compare the ORR of RO7247669 and the active comparator at the two-sided significance level of 20%, stratified by the protocol-defined stratification factors.
 
PFS based on RECIST
 
PFS defined as the time from randomization to the first occurrence of progression as determined by the Investigator according to RECIST v1.1 or death during the treatment period or within on study (i.e., within 60 days of the last study treatment tumor assessment) after treatment discontinuation, whichever occurs first. Participants who have not experienced disease progression at the time of analysis and who have not died during the treatment period or within 60 days of the last tumor assessment after treatment discontinuation will be censored at the time of the last tumor assessment. Participants with no post-baseline tumor assessment will be censored at the date of randomization.
 
The requirement that participants without a radiographic disease progression per RECIST v1.1 are still followed for the tumor assessments until progression or when the participant starts a new anti-cancer therapy (whatever occurs first), means that:

Endpoint	Statistical Analysis Methods
	
- intercurrent events of treatment discontinuations in absence of disease progression per RECIST 1.1 do not per se censor the PFS observation, since the participant will still undergo tumor assessments (treatment policy strategy)
 
- intercurrent events of new anticancer therapy imply instead that the PFS observation is censored at the last available tumor assessment before the new anticancer treatment starts, therefore assuming that participants who experience this intercurrent event have the same risk as those who did not (hypothetical strategy).
 
PFS will be compared between treatment arms with use of the stratified log-rank test.
 
The HR and its 95% CI for PFS will be estimated using a stratified Cox proportional-hazards model. Kaplan-Meier methodology will be used to estimate the median PFS for each treatment arm, and Kaplan-Meier curve will be constructed to provide a visual description of the difference between treatment arms.
 
DoR based on RECIST
 
DoR is defined as the time from the first occurrence of a documented objective response to disease progression according to RECIST v1.1 or death from any cause, whichever occurs first.
 
The analysis of DoR will include only participants who achieved an objective response to study treatment. DoR will be estimated using the Kaplan-Meier methodology. As the determination of DoR is based on a non-randomized subset of participants, no formal hypothesis testing will be performed.
 
Proportion of participants reporting clinically meaningful improvements in PRO measures
 
The proportion of participants in each treatment group reporting clinically meaningful improvement (defined as ≥ 10 points) in global health status/quality of life, emotional functioning, social functioning and dysphagia as measured by the EORTC QLQ-C30, IL-97, and OES-18 will be computed.
 
An estimate of this proportion for each treatment group as well as of the difference between proportions of each experimental arm compared to the active comparator will be computed along with its 95% CI.

CI = Confidence interval; CR = Complete response; DCR = Disease control rate; DoR = Duration of response; EORTC = European Organisation for Research and Treatment of Cancer; HR = Hazard ratio; IL97 = Item Library 97; OS = Overall survival; PFS = Progression-free survival; PR = Partial response; PRO = Patient-reported outcomes; RECIST = Response evaluation criteria in solid tumors.

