4.1.4 Scientific Rationale for Study Design

The study rationale is provided in Section 2.1.

In this study, the primary efficacy endpoints will be OS. This study will test the hypothesis that treatment with RO7247669 will prolong OS compared to treatment with nivolumab. Improvement in OS is generally accepted as the best measure of clinical benefit for patients with solid tumors. Prior studies with anti-PD1 treatments in 2L CPI-naïve ESCC showed inconsistent results for other commonly used endpoints such as ORR and PFS, which do not necessarily correlate with the observed OS benefits.

This study is blinded. Investigators, site staff, and participants will be unaware of the treatment allocation. Rationale for the blinded design is reducing potential bias in the assessment of disease recurrence/progression, PROs, and safety.

Nivolumab was chosen as active comparator for this study (Section 2.2.5). Given the positive data and approval of nivolumab for patients with ESCC after prior fluoropyrimidine- and platinum-based chemotherapy, independent of PDL1 expression, nivolumab was considered the best comparator for the anticipated patient population in this study.

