6.3 MEASURES TO MINIMIZE BIAS: RANDOMIZATION AND BLINDING

6.3.1 Method of Treatment Assignment

This is a Phase II, randomized, blinded, active-controlled study. After written informed consent has been obtained and eligibility has been established (including determination of tumor PD-L1 status by central testing), the study site will obtain the participant's identification number and blinded treatment assignment from the interactive response system (IxRS). An IxRS User Guide will be provided to each site.

Using a permuted-block randomization method, participants will be randomized to receive either RO7121661, RO7247669, or nivolumab in a [REDACTED] randomization ratio or – after the decision to stop enrollment into the RO7121661 arm – to receive either RO7247669 or nivolumab in a [REDACTED] randomization ratio.

Eligible participants will be stratified by the following criteria:

- [REDACTED]
- [REDACTED]
- [REDACTED]

These stratification factors were chosen because of their known or suspected potential to affect prognosis of treatment outcome with anti-PD1 treatment in ESCC. Prospective stratification by these factors will minimize differences in the three treatment arms due to sources other than the study drug.

Participants should receive their first dose of study drug on the day of randomization or at the latest on the day after randomization.

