8.2.5 Royal Marsden Hospital Risk Score

The Royal Marsden hospital risk score will be derived at screening for each participant ([Arkenau et al. 2008](#)). This risk-based score is derived from:

- Lactate dehydrogenase (LDH) $\leq ULN = 0$ versus LDH $> ULN = 1$
- Albumin ≥ 35 g/L = 0 versus < 35 g/L = 1
- Site of metastasis $\leq 2 = 0$ versus $> 2 = 1$.

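### The visible OS model names no baseline covariate beyond the stratification factors, although a prognostic risk score is collected on every participant at screening

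*Combined protocol and SAP*

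**What the plan says.** **Primary model.** The OS row of Table 9 (Section 9.3.2) gives Kaplan-Meier medians and a Cox hazard ratio with its "corresponding 95% confidence interval, stratified by the protocol-defined stratification factors". The row shows no redaction and lists no covariate. On who enters the model, the section says that "the statistical models will only include participants assigned to RO7247669 and nivolumab".

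**Stratifiers.** Section 6.3.1 introduces them with "Eligible participants will be stratified by the following criteria", followed by three redacted bullets. It says they were picked for their known or suspected bearing on prognosis. Section 4.1 leaves one word legible (previous). Inclusion criterion 8 requires a central PD-L1 result before stratification, so PD-L1 status is probably another.

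**Royal Marsden score.** Section 8.2.5: "The Royal Marsden hospital risk score will be derived at screening for each participant". It adds one point each for LDH above the upper limit of normal, albumin below 35 g/L, and more than two sites of metastasis. Section 9 does not mention it.

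**Two randomisation schemes.** Section 6.3.1 describes a three-arm scheme and, "after the decision to stop enrollment into the RO7121661 arm", a two-arm scheme. Both ratios are redacted.

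**Purpose.** Section 4.1.4 says: "This study will test the hypothesis that treatment with RO7247669 will prolong OS compared to treatment with nivolumab". Section 4.1 speaks of superiority. Section 9.1 instead gives estimation of the hazard ratio as the primary purpose.

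**The concern.** In a Cox model, omitting a prognostic baseline variable moves the treatment hazard ratio towards 1 even under perfect randomisation, and the test loses power. The score is collected on everyone before treatment, so using it needs no new data. If it predicts survival here and is not already a stratifier, the plan gives up sensitivity on its primary endpoint in a fairly small trial, for nothing in return.

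**Working it through.** **Inputs from the protocol.** Planned enrolment was 255 in three arms (Section 9.1). Median OS on PD1 inhibitors is 8.3 to 10.9 months (Section 2.3). The re-estimated sample size, OS event count, target hazard ratio, both ratios and any OS significance level are redacted or not given, so there is no planned figure to reproduce.

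**Assumptions.** 255 / 3 = 85 per arm, so 170 in the two arms. Deaths in 70% of them: 0.70 × 170 = 119. Control median 10.9 months. One binary stratifier. Score distribution 30/40/20/10% for 0/1/2/3. Score hazard ratio per point of 1.0 (not prognostic), 1.3, 1.6 or 2.0. True, score-conditional treatment hazard ratio of 0.70 or 0.65.

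**Benchmark (Schoenfeld, 1:1).** Power = Φ(√D/2 × |ln HR| − z). With D = 119 and HR 0.70: √119/2 = 5.454 and 5.454 × 0.3567 = 1.945.
- Two-sided 5%: Φ(1.945 − 1.960) = 49%.
- Two-sided 20%: Φ(1.945 − 1.282) = 75%.

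The simulation with a non-prognostic score gives 46.5% and 71.9%, close enough to rely on.

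**Adding the score.** 1000 simulated trials per row. Each trial is analysed with the stratified Cox model without the score, then with it.

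| True HR | Score HR per point | Average HR, without → with | Power at 5%, without → with | Power at 20%, without → with |
|---|---|---|---|---|
| 0.70 | 1.0 | 0.700 → 0.699 | 46.5% → 46.5% | 71.9% → 72.7% |
| 0.70 | 1.3 | 0.713 → 0.705 | 42.5% → 45.0% | 70.3% → 71.7% |
| 0.70 | 1.6 | 0.720 → 0.697 | 41.8% → 48.4% | 68.2% → 73.5% |
| 0.70 | 2.0 | 0.739 → 0.693 | 37.1% → 50.0% | 62.9% → 75.1% |
| 0.65 | 1.3 | 0.655 → 0.647 | 63.6% → 65.4% | 83.0% → 83.8% |
| 0.65 | 1.6 | 0.678 → 0.648 | 55.1% → 64.0% | 79.5% → 84.9% |
| 0.65 | 2.0 | 0.705 → 0.653 | 46.6% → 61.2% | 72.7% → 85.3% |

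The Monte Carlo standard error of one power estimate is about √(0.43 × 0.57 / 1000) = 1.6 points. Both models see the same trials, so the differences are firmer than that, but the smallest gains should not be read to the decimal.

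**Randomisation scheme.** Same set-up, half the patients in each scheme, true treatment hazard ratio 1:
- Same ratio in both schemes (1:1 or 2:1 throughout), hazard ratio between schemes 0.8 to 1.5: the pooled estimate is 0.995 to 1.011. There is nothing to remove.
- Ratio changed between 1:1 and 2:1, hazard ratio between schemes 0.8 or 1.25: pooled estimate 0.953 to 1.036. With 1.5 it is 0.918 or 1.075. Stratifying by scheme returns these to 0.981 to 1.005.
- Cost of the extra stratum at equal ratios: in the runs with true hazard ratio 0.65 or 0.70, power at 5% changed by between +0.4 and −1.6 points.

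**The case against.** A reader might infer that the plan is known to omit the score. The documents do not support that. All three stratifiers are redacted and at least one is wholly unreadable, so the score could be among them. Two features make it unlikely but do not settle it: the score sits under safety assessments, and Section 6.3.1 singles out PD-L1, not the score, as needed before assignment. Section 9.3.1 has an open-ended list of baseline characteristics, and Section 9.3 defers detail to a separate technical document. The accurate statement is therefore that no visible analysis names the score.

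The documents also do not give its prognostic strength in second-line ESCC. The one source cited for it is, by its title, about phase I patients. At 1.3 per point the gain is 1 to 3 power points, and with no prognostic value it is nil. This stands, and it is why the result is a range.

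Stratifying only by the randomisation factors is a standard analysis, and the unadjusted hazard ratio is not biased for its own target. Adjustment changes the target to a hazard ratio conditional on the score, whereas Table 4 says only that the summary measure is hazard ratios. This stands too: the change must be declared.

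None of this removes the case for prespecifying a cheap covariate, because the recommendation lapses if the score is already a stratifier.

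**Conclusion.** The point holds as a low-cost improvement to the primary model, not as an error in it. If the score is prognostic and not already a stratifier, adding it gains roughly 1 to 15 power points across the settings tried (0.8 points at hazard ratio 0.65, score 1.3, 20% level; 14.6 points at hazard ratio 0.65, score 2.0, 5% level). The unadjusted hazard ratio lies nearer 1 by 0.008 to 0.052. This rests on the assumed 170 patients, 119 deaths and score distribution.

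Two stronger readings are tempting and should be resisted.

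- **Pooling across version 3 confounds the OS hazard ratio.** That needs both a changed RO7247669:nivolumab ratio and a prognostic difference between schemes. Both ratios are redacted, and 255 over three arms fits 1:1:1, though it does not prove it. If the ratio between these two arms stayed the same, there is no such bias.
- **OS is held to a stricter bar than ORR**, because ORR is compared "at the two-sided significance level of 20" per cent while OS has only a 95% interval. No visible text makes that interval a decision rule, the sizing text in Section 9.1 is redacted, and carrying the ORR level over to OS would be a preference. What remains is a wording conflict: Sections 4.1 and 4.1.4 promise superiority and a hypothesis test, while Section 9.1 describes estimation.

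**What to change.** In the OS row of Table 9:

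1. Add the Royal Marsden score (0 to 3) as a prespecified covariate in the stratified Cox model, unless it is already a stratification factor.
2. State there and in Table 4 that the hazard ratio is then conditional on the score as well as the stratifiers.
3. Give a rule for missing score components, such as a separate missing category. Albumin is an eligibility item, LDH is in the screening chemistry panel and sites come from the screening scans, so few should be missing.
4. Keep the stratified hazard ratio without the score as a supporting analysis.
5. Add randomisation scheme (before or after version 3) as a stratum only if the RO7247669:nivolumab ratio changed. Otherwise no such term is needed.

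Separately, reconcile Sections 4.1 and 4.1.4 with Section 9.1 on whether OS is tested or estimated.

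The cost is wording; no new data are collected. The price is the declared change of target and the handling of a few incomplete scores. The wording should be settled before the interim analysis, because Section 9.4 gives sponsor study personnel full unblinded access at that point and a covariate chosen afterwards would be open to challenge.
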